### Project description for a human trial on colorectal cancer prophylaxis:

#### Aim:

Primary aim:

To investigate for a possible inhibitory effect from carrot juice on the recurrence of excised adenomas and, on the formation of metachronous adenomas in patients who are enrolled in a follow up program after resection of high risk colorectal adenomas.

An inhibitory effect of carrot juice will be measured by a combined endpoint of total number of recurrent adenomas multiplied with mean size of recurrent adenomas in the active arm or the placebo group. This difference will be significant if carrots mediate a 20% reduction in both size and numbers.

If the difference in number of polyps is 40 % or more, we will be able to prove this to be significant. If the difference in polyp size is larger than 40 % we will also achieve statistical difference between the 2 groups.

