#### **Outcome measures**

Primary:

• The primary outcome is the number and size of polyps found at the one-year follow up colonoscopy in the treatment arm and in the placebo arm.

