#### Sample size:

Patients seen at the one-year follow up after high risk polyps have 40 % chance of having new polyp/polyps at the colonoscopy. The difference in polyp number found between treatment and control in rats was 40%. The difference in large polyps was 80 % but this is based upon small numbers. The possible effect in humans is unknown. A difference of 10 % or 20 % would be of clinical interest. To test for a difference of 20 % would demand the enrolment of 1248 persons, which is not realistic.

The study is dimensioned to prove a significant difference in number of polyps after 3 years and a significant difference in the combined endpoint (number x size) after 1 year of treatment. The expected effect in number of adenomas in the active and the control arm is a > 20% reduction (corresponding to a 50% relative reduction).

- 1. The recurrence rate is estimated to 40%
- 2. The acceptance rate to participate is 55%.
- 3. The exclusion rate is 20%
- 4. The total drop-out rate is expected to be 20%.
- 5. The drop-out patients are estimated to an average 6 months participation.

We assume 80% power and a standard deviation of 5%. Using a two-sided X2-test, a total of 726 patients have to be invited with a minimum of 328 patients to complete the trial. Due to the expected variability of the factors above, we aim to include a total of 400 patients equally to either case or controls. Achieving this number of included patients will require approximately 1.000 possible candidates to be invited. The combined capacity of the included centers is 1.600 eligible patients per year. Therefore, we estimate that the enrollment can be completed within 12 months.

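### The protocol's sections disagree on whether polyp size is primary by itself, and a size-only comparison sets groups selected after randomisation against each other, with bias possible in either direction

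*Protocol*

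**What the plan says.** The protocol describes the primary measure in three places.

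- **Aim (primary aim).** The effect is measured by a "combined endpoint of total number of recurrent adenomas multiplied with mean size of recurrent adenomas", by arm. The next sentence says when this would be detected: "This difference will be significant if carrots mediate a 20% reduction in both size and numbers". Two further statements follow, each claiming significance for one component if it differs by about 40%. The one for size reads: "If the difference in polyp size is larger than 40 % we will also achieve statistical difference between the 2 groups".
- **Outcome measures.** "The primary outcome is the number and size of polyps found at the one-year follow up colonoscopy". Neither the product nor any other combining rule is mentioned, and the lesions counted are polyps, not adenomas.
- **Sample size.** The one-year sizing is for "a significant difference in the combined endpoint (number x size) after 1 year of treatment". Number alone is assigned to three years, and size alone is not mentioned. Patients at this follow-up "have 40 % chance of having new polyp/polyps at the colonoscopy", and the planned effect on number is given as 50% relative.

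The protocol gives no mean or standard deviation of adenoma size. It does not say how a patient without polyps enters a size comparison.

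**The concern.** A reader of Outcome measures and the last sentence of the primary aim would conclude that size may be tested between arms on its own. A reader of Sample size would conclude that only the product is tested at one year. These are different analyses and can give different answers.

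The size-only version has a structural problem. A patient without a polyp has no size, so the comparison is restricted to patients with one. Whether a patient has a polyp is decided after randomisation and is what the treatment is supposed to influence. The two groups compared are then no longer the randomised groups. A difference in mean size can arise purely from which lesions remain, so it cannot be read as an effect on growth.

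**Working it through.** **The plan's own figures.** The claim about a 40% size difference cannot be reproduced, because no mean or spread of size is given. The 5% standard deviation under Sample size has no stated variable or unit. The stated minimum of 328 completers comes from a chi-square test, which concerns a proportion and says nothing about size. Whether 328 is right is a separate matter.

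**Who has a size value.** Inputs from Sample size: 400 patients split equally, 20% drop-out, 40% recurrence, 50% relative reduction. The last two are read here as 40% versus 20% of patients with a polyp.

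- Completers per arm: 200 × 0.80 = 160.
- Control patients with a size: 160 × 0.40 = 64.
- Active patients with a size: 160 × 0.20 = 32.

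**What the size-alone claim would need.** Assume two-sided 5% (alpha is not stated) and 80% power. The largest coefficient of variation (CV) at which a 40% difference in means is detectable is 0.40 / [2.80 × √(1/n₁ + 1/n₂)].

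- 64 versus 64: 0.40 / (2.80 × 0.177) ≈ 0.81.
- 64 versus 32: 0.40 / (2.80 × 0.217) ≈ 0.66.
- 160 versus 160, if every patient had a size: 0.40 / (2.80 × 0.112) ≈ 1.28.

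The protocol gives nothing to show which side of these limits adenoma size falls.

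**What the product is.** With N adenomas of summed size S, number × mean size = N × (S/N) = S. The product is total adenoma size, and a patient without adenomas adds zero. A 20% fall in both components gives 0.80 × 0.80 = 0.64, a 36% fall in S.

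**How the measures move.** Lesion sizes are assumptions. No lesion changes size in any row; some are only prevented. The rat pattern is the Background's 35% fewer early and 80% fewer large lesions.

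| Controls, per 100 adenomas | Effect | Number | Sum (mm) | Mean (mm) |
|---|---|---|---|---|
| 80 of 4 mm, 20 of 12 mm | half of small prevented | 100 → 60 (−40%) | 560 → 400 (−29%) | 5.60 → 6.67 (+19%) |
| 80 of 4 mm, 20 of 12 mm | rat pattern | 100 → 56 (−44%) | 560 → 256 (−54%) | 5.60 → 4.57 (−18%) |
| 70 of 4 mm, 30 of 12 mm | rat pattern | 100 → 51.5 (−48.5%) | 640 → 254 (−60%) | 6.40 → 4.93 (−23%) |

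Example for row 1: 40 × 4 + 20 × 12 = 400, and 400/60 = 6.67.

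Over small-lesion shares of 50–80% and sizes of 4/12, 5/15 or 3/10 mm:

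- Preventing 40% of small lesions moves number by −20% to −32%, mean size by +12.5% to +16%, and the sum by −9% to −23%.
- Preventing 50% moves them by −25% to −40%, +17% to +22%, and −11.5% to −29%.

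**Simulation.** Assumptions: 160 completers per arm, 40% of controls with polyps, lognormal sizes with median 5 mm, and half of lesions under 10 mm prevented. Number fell 43%, mean size rose 15% and the product fell 34%. Size among patients with polyps was significantly worse in 13% of trials. The per-patient product was significantly better in 71%.

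**The case against.** The strongest reply is that the protocol already names a sound quantity. Aim and Sample size both use the product, which equals total adenoma size, gives polyp-free patients zero, and falls in every scenario above. On that reading, Outcome measures is shorthand for the product, and how a supporting size analysis scores polyp-free patients can wait for the statistical analysis plan. This largely stands, and the absence of a scoring rule is not itself the point. What the reply does not cover is the sentence claiming significance for size alone, or an outcome list that names size without the product. Both are in the protocol and conflict with its sizing.

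Two stronger readings are tempting and are not supported:

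- **That effective juice would fail a requirement of 20% in both.** There is no such requirement. The sentence says when the product would be detectable; nothing makes a 20% fall in each component a condition of success. Its weakness is only that it assumes number and size fall together.
- **That effective juice would look harmful.** This holds only if it prevents mainly small adenomas, and then only on size, not on the product. The rat figures in the Background point the other way and would lower mean size.

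**Conclusion.** The point holds as an inconsistency in the primary measure, together with a size-only claim that randomisation cannot support. The inconsistency and the dependence of size on having a polyp follow from the text alone. The 64 versus 32 rests on the protocol's planning rates. The shifts in mean size, about +12.5% to +22% when 40–50% of small adenomas are prevented and −18% to −23% under the rat pattern, rest on assumed lesion sizes. They show that the distortion can go in either direction; they do not predict this trial's result. The product endpoint does not have this defect, but as arm total times arm mean it is one figure per arm and needs a per-patient form before it can be tested. This should be corrected; it does not undermine the design.

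**What to change.** 1. In Aim, Outcome measures and Sample size, define one primary measure: the sum of adenoma diameters per patient at the one-year colonoscopy, 0 mm if none is found, for every randomised patient who has that examination. This keeps the intended number × size quantity and makes it testable per patient.
2. Delete the statement that a size difference above 40% would be significant by itself.
3. Restate the sentence on 20% in both as a detectable reduction in the summed measure, with the assumed distribution behind it. The 36% from 0.80 × 0.80 should not be carried over unchecked: in the simulation above, 20% fewer and 20% smaller lesions gave a significant per-patient product in only about 32% of trials. That share depends on the assumed sizes and the test.
4. Report mean size among patients with polyps as descriptive only.

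The colonoscopy data are unchanged and only wording is affected. The cost is the separate confirmatory claim on size. It would matter most if the juice only shrank adenomas: with lesions 40% smaller and none prevented, the simulated per-patient product was significant in about 19% of trials, against nearly all for size among patients with polyps.

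### The Aim, Outcome measures and Sample size sections do not agree on which comparison, at which time point, decides the primary aim, so the false-positive rate of the main claim is left open

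*Protocol*

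**What the plan says.** Three sections of the protocol bear on what decides the primary aim.

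- **Aim, primary aim.** The measure is introduced as one quantity: "An inhibitory effect of carrot juice will be measured by a combined endpoint of total number of recurrent adenomas multiplied with mean size". The text says this will be significant if both components fall by 20%. Two further sentences follow. On number: "If the difference in number of polyps is 40 % or more, we will be able to prove this to be significant". On size: "If the difference in polyp size is larger than 40 % we will also achieve statistical difference between the 2 groups". No time point is attached to any of the three.
- **Outcome measures, primary.** "The primary outcome is the number and size of polyps found at the one-year follow up colonoscopy". The product is not mentioned, and nothing says whether one or both of number and size must differ.
- **Sample size.** "The study is dimensioned to prove a significant difference in number of polyps after 3 years", and also for "a significant difference in the combined endpoint (number x size) after 1 year of treatment". The calculation lists a 40% recurrence rate and is made "Using a two-sided X2-test", which is a test for proportions and not for number, size or their product.

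The secondary outcomes include the number of patients with polyps in each arm. The protocol states no significance level, testing order or alpha split, and no rule on which result makes the trial positive.

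**The concern.** A trial has a known false-positive rate only if the comparison that decides it is fixed beforehand. Here the primary-aim text describes three differences as capable of reaching significance, and the other two sections do not narrow them to one. An analysis testing only the product would be consistent with the protocol. So would one testing number and size separately, or all three, and claiming inhibition on whichever falls below 0.05.

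A later analysis plan can set models and handling rules. It would, however, be choosing among measures that the protocol has already put forward under the primary aim and the primary outcome. If that choice is made or changed after the code is broken, the result is open to the charge that the measure was selected because it worked.

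**Working it through.** **Inputs from the protocol (Sample size).** Recurrence rate 40%; 328 completers, so 164 per arm; 400 randomised 1:1 with 20% drop-out, so 400 × 0.80 / 2 = 160 per arm; a two-sided test.

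**Inputs not in the protocol, assumed.** Alpha 0.05 per test; correlation of number with size from 0 to 0.5; number of polyps per affected patient and spread of sizes (varied); any one significant result counts as success.

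**Step 1. The plan's own figure.** No error rate is stated, so there is none to reproduce. The only related figure is 328 completers. For 40% against 20%, 80% power and an assumed two-sided 0.05:

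n per arm = [1.960 × √(2 × 0.30 × 0.70) + 0.842 × √(0.40 × 0.60 + 0.20 × 0.80)]² / 0.20² = (1.270 + 0.532)² / 0.04 ≈ 81.2, so 82.

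That is 164 in total, and 328 is exactly twice that. The figure is not reproduced from the stated inputs. This is a separate matter; 328 serves here only as the trial size.

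**Step 2. The sections by measure.**

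| Measure | Aim | Outcome measures | Sample size |
|---|---|---|---|
| Number × mean size | the measure of effect, no time point | not primary as such | 1 year |
| Number alone | can be proven at 40%, no time point | primary, 1 year | 3 years |
| Size alone | can reach significance above 40%, no time point | primary, 1 year | not mentioned alone |
| Recurrence (proportion) | not mentioned | patients with polyps is secondary | basis of the chi-square calculation |

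No measure has the same role and time point in all three sections.

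**Step 3. Bounds.** Two independent tests at 5%: 1 − 0.95² = 9.75%. Three independent tests: 1 − 0.95³ = 14.3%; the Bonferroni ceiling is 3 × 5% = 15%. The product is a function of the other two measures, so the three-test figure must fall below 14.3% when number and size are themselves independent.

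**Step 4. Normal approximation.** Since log(number × size) = log number + log size, the product's test statistic is a weighted sum of the other two: Z_P = (Z_N + w·Z_S) / √(1 + w² + 2wρ). Here ρ is their correlation and w the ratio of their standard errors on the log scale. The probability that any of |Z_N|, |Z_S|, |Z_P| exceeds 1.96 under no effect (1,000,000 draws) is:

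| ρ | w = 0.5 | w = 1 | w = 2 |
|---|---|---|---|
| 0 | 11.2% | 11.5% | 11.2% |
| 0.3 | 10.4% | 10.6% | 10.4% |
| 0.5 | 9.5% | 9.6% | 9.5% |

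**Step 5. Patient-level null simulation.** 164 per arm, 40% of patients with polyps, mostly Mann-Whitney tests, with polyps per affected patient, size spread and correlation varied:

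- size compared only among patients with polyps: 10.2% to 11.5% (2,500 trials per setting);
- polyp-free patients counted as size 0: 6.1% to 7.7% (1,500 trials per setting). All three measures then depend largely on whether a patient has any polyp, so they overlap heavily.

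A separate simulation with 160 per arm and 1.5, 2 or 3 polyps per affected patient (4,000 trials each) gave 11.2%, 11.9% and 11.8%. This is the upper end of the range.

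**Step 6. Check of the remedy.** With one confirmatory test, or a fixed order in which each test needs the previous one to succeed, a false claim under no effect requires the first test to reject, so the rate is 5%. Splitting alpha, 0.05 / 3 = 0.0167 per test, also keeps it at or below 5%.

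**The case against.** The strongest reply is that the Aim section does name one measure, the product, and that the two 40% sentences only say how large a difference would be detectable. Sample size supports this in part, since at one year it dimensions only the product. This reading is fair for the Aim section taken alone. It does not carry over to Outcome measures, which makes number and size primary at one year and leaves the product out. Speaking of proof for number alone, under the primary aim, also invites a claim from a component.

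A second reply is that alpha, testing order and multiplicity commonly belong in the analysis plan, which is not shown. That stands: their absence is not the finding. The finding is that the protocol's own sections disagree on measure and time point.

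A reader might go further and infer that the protocol sets up three co-equal one-year tests with a false-positive rate of 11-12%, more than double the nominal level. The documents do not support this. The Aim gives no time point, Sample size places number at 3 years, and no section states an alpha or says that one success is enough. The 11-12% is the upper end of a range that rests on assumptions.

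A reader might also count the chi-square comparison as a fourth route, which would raise the simulated figure to 13-14%. That does not hold either: the number of patients with polyps is listed as a secondary outcome, and the chi-square test is named only in the sample-size calculation.

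**Conclusion.** The concern holds as a contradiction in the primary comparison, not as a demonstrated decision rule. If product, number and size were each tested at an assumed two-sided 5% and any one counted as success, the false-positive rate would be roughly 10-11%. It would lie between about 6% and 12% according to the correlation of number with size and whether polyp-free patients enter the size comparison as zero. It exceeded 5% under every assumption tried. If the sponsor in fact means to test only the product, the rate is 5% and the fault is one of wording. The protocol should be corrected in either case, because as written it cannot tell the reader which of these applies.

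**What to change.** Before the code is broken, which the Randomization section places after the last patient's last dose:

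1. Name one confirmatory comparison at one year, at two-sided 5%, in identical terms in Aim, Outcome measures and Sample size. Aim and Sample size both point to number × size.
2. State whether it is defined per patient. The Aim defines it per arm, where total number × mean size is simply the summed size of all adenomas in that arm. A per-patient version would redefine the endpoint and should be declared as such.
3. Test number and then size in a fixed order after the product, or report both as supportive with confidence intervals.
4. Reword the two 40% sentences as detectable differences, not as separate proofs.
5. Label the 3-year comparison of number as secondary.

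The cost is wording in the protocol and any analysis plan, with no extra patients required by this change. The real downside is that a result on number or size alone could not be claimed as confirmatory if the product comparison failed.

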### Secondary aim:

Compliance and side effects will be registered through questionnaire and diary and we will identify critical pathways in patient acceptability and compliance of carrot intake from a diary.

#### **Outcome measures**

Primary:

• The primary outcome is the number and size of polyps found at the one-year follow up colonoscopy in the treatment arm and in the placebo arm.

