#### Abstract:

**Background**: Carrot cultivars with a high content of falcarinol and falcarindiol have a strong antineoplastic effect in primed rats. The necessary corresponding blood concentration can easily be obtained in humans. High intake of carrots has been shown to reduce bowel cancer in humans in prospective cohort studies, and carotenes have been shown not to have any effect. A prophylactic effect against other cancers in humans especially of the lung and pancreas has also been indicated (1).

Patients who had polyps resected that are considered high risk will be offered a follow up (FU) colonoscopy after 1 year and after 3 years according to national guidelines. At this FU, about 30-40% of them will present with local recurrence or new polyps on colonoscopy.

The study will follow the new national guidelines with the approved acceptable timeframe adjustments, this meaning we will conduct the control colonoscopy at 3 months for piecemeal resection and a full colonoscopy at 1 year for all the patients involved in the study.

More than 90% of bowel cancers arise from adenomas and therefore prevention of adenomas is effective in preventing colorectal cancer.

**Method**: We aim to include and randomize 400 patients at the four institutions into two groups of equal size. It is expected that 80% of those will comply throughout one year of treatment. The patients are randomized blindly into one group receiving daily 100 ml active carrot juice and one group receiving 100 ml placebo. This amount has been calculated from our experiments in rats to be a sufficient volume as measured by serum concentration. After 1 year, we will register the number and sizes of polyps diagnosed in the 2 groups.

The primary aim is to investigate for a carrot-medicated inhibition of neoplastic transformation and growth in high risk humans.

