# Methodology

# Design of the intervention

The trial will be conducted as a double-blind controlled, randomized study. Patients, who, at colonoscopy, had high-risk adenomas, are randomized in 2 arms. One arm will receive 100 ml of carrot juice with a high concentration of falcarinol and falcarindiol daily for 1 year and the other arm will receive 100 ml of placebo juice daily for 1 year until their follow up full colonoscopy. The placebo juice will be produced from commercially available artificial juice without Falcarinol or Falcarindiol. At the follow up colonoscopy, another standardized report will be fulfilled by the endoscoper, containing information about recurrence, the number of polyps, polyp size and risk stratification (no-, low-, medium, high risk polyps or cancer).

The compliance will be registered through diaries/calendars and patients will be followed through the entire period, regardless of their level of compliance. Patients with compliance drop-outs will be encouraged to reenter and complete with as high a compliance as possible.

Patients will be informed that they will receive a call after 1 month from each appointment, where their questions and concerns will be answered.

After the first colonoscopy, patients will be offered inclusion into the trial. If the resection of the high-risk polyp took place in the first colonoscopy, the patient will call the project nurse if he/she is interested in participating in the study and make an appointment for being enrolled in the project. If the resection will take place in a specialized unit where a second colonoscopy will be performed for the resection, then they will give their final answer at this appointment.

The patient will collect 8 liters of juice/placebo every 2 months at a visit at the clinic. At this visit, they will be interviewed for compliance, intake of additional carrots/carrot containing products and possible side effects. If the project nurse assesses the patient as non-compliant then he/she will be excluded from the study.

Each participant will have 6 visits and the 4 institutions will in total have 2400 visits, which is approximately 600 visits in two years at each institution. Visits can be organized in weekly group sessions. Compliance diaries and questionnaires will be explained and collected according to written instructions.

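### The primary endpoint is set on adenomas in the Aim but on polyps of any kind in Outcome measures, and the sample size mixes the two

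*Protocol*

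**What the plan says.** The protocol describes the primary lesion in several places, and they do not agree.

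- **Aim.** The primary aim is a possible "inhibitory effect from carrot juice on the recurrence of excised adenomas and, on the formation of metachronous adenomas". The measure is a "combined endpoint of total number of recurrent adenomas multiplied with mean size of recurrent adenomas". Both are about adenomas.
- **Aim, next paragraph.** The detectable difference is given for polyps: "If the difference in number of polyps is 40 % or more, we will be able to prove this to be significant".
- **Outcome measures, Primary.** "The primary outcome is the number and size of polyps found at the one-year follow up colonoscopy". Histology is not mentioned.
- **Abstract.** "After 1 year, we will register the number and sizes of polyps diagnosed in the 2 groups".
- **Sample size.** The 40% one-year rate is given for new polyps and repeated as a recurrence rate with no lesion named. The planned effect is given for adenomas: "The expected effect in number of adenomas in the active and the control arm" is put at a reduction of more than 20%, described as 50% in relative terms.
- **Design of the intervention.** The follow-up report records "the number of polyps, polyp size and risk stratification (no-, low-, medium, high risk polyps or cancer", so it has a class for polyps without risk.

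No section says that *polyp* means adenoma, or limits the primary count to lesions confirmed as adenomas. Pathology results are among the data taken from patient records, and a secondary outcome grades polyps by dysplasia and cancer.

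**The concern.** The lesion that is counted is part of the definition of the primary endpoint, and the protocol gives two. The same data can therefore yield two primary results with different event counts, and nothing says which one decides the trial.

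The choice also affects sensitivity. The Abstract states the aim as inhibiting neoplastic transformation and growth. If the juice has no effect on non-neoplastic polyps, counting them adds equal numbers to both arms on average and moves the ratio of counts towards 1. They enter the size component too.

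The planning figures have the same problem: a control rate stated for polyps is paired with an effect stated for adenomas.

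**Working it through.** **The plan's own figure.** For 40% versus 20%, two-sided 5% (assumed, since the protocol states no alpha) and 80% power, the two-proportion formula gives 82 per arm, 164 in total. The stated minimum of 328 completers is not reproduced; it equals 2 x 164. That is a separate matter, and 328 is not used below.

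**Inputs**
- Completers per arm: 400 x (1 - 0.20) / 2 = 160 (Sample size).
- Mean count matching 40% of patients with at least one lesion, under a Poisson model: -ln(1 - 0.40) = 0.511.
- True adenoma reduction r: 40% (the detectable difference in the Aim) or 50% (Sample size).
- Share s of polyps in the control arm that are not adenomas: **not in the protocol**; assumed 20%, 30% or 40%.
- Effect of the juice on those polyps: assumed none.

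**Formulas**
- Reduction seen in all polyps = r x (1 - s). For r = 40% this is 32%, 28%, 24%; for r = 50% it is 40%, 35%, 30%.
- SE of the log rate ratio = sqrt(1/(160 m0) + 1/(160 m1)), where m0 and m1 are the mean counts in the control and active arms.
- Power = Phi(|ln(m1/m0)| / SE - 1.96).

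**Two readings of the 40% rate**
- Reading A, any-polyp rate: all-polyp control mean 0.511, adenoma control mean 0.511 x (1 - s).
- Reading B, adenoma rate: adenoma control mean 0.511, all-polyp control mean 0.511 / (1 - s).

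**Worked case, s = 20%, r = 40%**
- A, all polyps: 0.511 vs 0.511 x 0.68 = 0.347; SE 0.174; z = 0.386/0.174 = 2.22; power 60%.
- A, adenomas: 0.409 vs 0.245; SE 0.202; z = 0.511/0.202 = 2.53; power 72%.
- B, all polyps: 0.639 vs 0.434; SE 0.156; z = 2.48; power 70%.
- B, adenomas: 0.511 vs 0.307; SE 0.181; z = 2.83; power 81%.

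**All cases** (power in %; losses in percentage points, from unrounded values)

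| r | s | A: all polyps | A: adenomas | Loss | B: all polyps | B: adenomas | Loss |
|---|---|---|---|---|---|---|---|
| 40% | 20% | 60 | 72 | 11 | 70 | 81 | 11 |
| 40% | 30% | 48 | 66 | 17 | 63 | 81 | 18 |
| 40% | 40% | 37 | 59 | 22 | 56 | 81 | 25 |
| 50% | 20% | 81 | 90 | 9 | 89 | 95 | 7 |
| 50% | 30% | 69 | 86 | 17 | 83 | 95 | 12 |
| 50% | 40% | 54 | 80 | 26 | 76 | 95 | 19 |

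These figures are for the count alone. The number-times-size endpoint cannot be powered from what the protocol gives.

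**The case against.** **The words may be used loosely.** The inclusion criteria require an adenoma above 20 mm, while the section on information from patient files describes the same criterion as a polyp above 20 mm. Grading polyps by dysplasia also suggests that neoplastic lesions are meant. This is a plausible reading, so the documents do not support inferring that the sponsor decided to count hyperplastic polyps. It does not remove the conflict: no section equates the terms, and the follow-up report includes a no-risk class.

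**Histological detail can be left to the SAP.** That holds for details such as lesions not retrieved. It does not hold for the lesion that defines the primary outcome, which the protocol fixes in two ways. An SAP that follows one section departs from the other.

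**The power loss can be overstated.** A reader might compare 81% with 60-37% and blame the whole drop on counting polyps. That is not like for like. The 81% applies to a mean of 0.511 that is all adenomas. If 40% is the any-polyp rate, limiting the count to adenomas also removes events, and power returns only to 72-59%.

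**On the planned chi-square the loss is milder.** If 40% is the any-polyp rate and only the adenoma part is halved, 160 per arm gives 87% power at a 20% non-adenoma share (40% vs 24%), 76% at 30% (40% vs 26%) and 62% at 40% (40% vs 28%). This stands: with a 50% relative reduction, a small share does little harm. The Sample size section itself says that differences of 10% or 20% would be of clinical interest.

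**Conclusion.** The inconsistency in the primary endpoint is certain from the text: adenomas in the Aim, polyps in the Abstract and Outcome measures, and both in Sample size. It should be settled before the code is broken, whatever the true adenoma share.

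The direction of the effect is conditional: towards no effect if the juice acts only on adenomas. The size is illustrative. With an assumed 20-40% of unaffected non-adenomas, Poisson counts and 160 per arm, counting all polyps costs about 11-25 points of power at a 40% adenoma reduction and about 7-26 points at 50%. The protocol gives neither the adenoma share nor the effect on other polyps, so it does not support a firm statement that the trial will be diluted by a given amount.

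**What to change.** - In Outcome measures, state that the primary outcome concerns histologically confirmed adenomas, including any cancer, at the one-year colonoscopy, taken from the pathology results already collected.
- Use that term consistently in the Abstract, Aim, Outcome measures and Sample size.
- Say which lesion type the 40% rate refers to, so that rate and effect are on the same lesion.
- Report all polyps as a supportive outcome.

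The cost is a wording amendment, with no new visits or data. There are two drawbacks. If 40% is the any-polyp rate, the primary count will contain somewhat fewer events than planned. Lesions not retrieved for histology will also need a default classification, fixed before unblinding.
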